|        |           | 
Section 6.2.4 Visit 31/Day 1093/Week 156 through Visit 43/Day 1765/Week 252 (+/-3 Days)
 
Section 6.2.5 End of Treatment Visit/Day 1821/Visit 44/Week 260 (+/-3 Days)
 
Section 6.2.6 Sub-Study Treatment Period (new)
 
Section 6.2.6.1 Sub-Study Visit 1a/Day 1a/Week 0a (<math>\pm 3</math> days) (new)
 
Section 6.2.6.2 Sub-Study Visit 2a/Day 29a/Week 4a (<math>\pm 3</math> days) (new)
 
Section 6.2.6.3 Sub-Study Visit 3a/Day 85a/Week 12a (<math>\pm 3</math> days) (new)
 
Section 6.2.6.4 Sub-Study Visit 4a/Day 169a/Week 24a (<math>\pm 3</math> days) (new)
 
Section 6.2.6.5 End of Study Visit (Last Dose+12 weeks), Early Termination Visit, and Unscheduled Visits (new)
 
Section 6.2.7 End of Study Visit (84 Days After Last Dose or 12 Weeks After Last Dose)
 
Section 6.2.8 Early Termination Visit
 
Section 6.2.10 Re-entry Visit (Main Study Only)
 
Section 7.2.3 Other Events that Require Accelerated Reporting to Sponsor
 
Section 8.2.3 Sub-Study Endpoints (new)
 
Section 8.3 Pharmacokinetic variable
 
Section 9.5.6 Analysis of the Sub-Study (new)
 
Section 9.5.6.1 Statistical Hypothesis for the Sub-Study (new)
 
Section 9.5.6.2 Justification of the Sub-Study Sample Size (new)
 
Section 9.5.6.3 Analysis Sets for the Sub-Study (new)
 
Section 9.5.6.4 Statistical Methods for the Sub-Study (new)
 |

| Change  | Rationale  | Section Title and Number  |
|---|--|---|
| 
The protocol was updated to remove the Kaplan-Meier survival curve from the primary analysis and the secondary endpoint of time to event. The time to event endpoints were used in the first-step analysis to support a regulatory submission. As the first-step analysis has been completed, the time-to-event endpoints and the Kaplan-Meier estimates are no longer needed and have been removed from statistical analysis.
 | 
For consistency with the statistical analysis plan (version 2.0).
 | 
Clinical Study Protocol Synopsis:
Statistical Plan
Section 8.2.2 Secondary Endpoints
Section 9.5.3 Efficacy Analysis
 |

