### 7.2.3. Other Events that Require Accelerated Reporting to Sponsor

The following events also require reporting to the sponsor (or designee) within 24 hours of learning of the event:

**Symptomatic Overdose of Study Drug:** Accidental or intentional overdose of at least 2 times the intended dose of study drug within the intended therapeutic window, if associated with an AE.

**Pregnancy:** Although pregnancy is not considered an AE, it is the responsibility of the investigator to report to the sponsor (or designee), within 24 hours of identification, any pregnancy occurring in a female patient during the study or within 12 weeks of the last dose of study drug. Any complication of pregnancy affecting a female study patient and/or fetus and/or newborn, must be reported as an SAE.

**Adverse Events of Special Interest:** AEs of special interest (AESIs) will be entered into the EDC system within 24 hours of identification. The site will also notify the Regeneron medical monitor of the AESIs within 24 hours of identification.

Adverse events of special interest in this study include:

- Anaphylactic reactions
- Systemic hypersensitivity reactions
- Helminthic infections
- Any severe type of conjunctivitis or blepharitis
- Keratitis
- Clinically symptomatic eosinophilia (or eosinophilia associated with clinical symptoms)

Additional AESIs for the sub-study using the new dupilumab drug product:

- Any serious or severe ISR or any ISR lasting longer than 24 hours.

Refer to the study reference manual for the procedures to be followed.

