#### 8.2.2. Secondary Endpoints

The secondary endpoints are:

- Key secondary endpoints
  - Incidence and rate (events per patient-year) of SAEs and AESIs
  - Proportion of patients with IGA = 0-1 at each visit
  - Proportion of patients with EASI-75 ( $\geq 75\%$  reduction in EASI scores from baseline of the parent study) at each visit
- Other secondary endpoints:
  - Proportion of patients with low disease activity state (eg, IGA  $\leq 2$ ) at each visit
  - Change and percent change from baseline in EASI score at each visit
  - Proportion of patients with EASI-50 ( $\geq 50\%$  reduction in EASI scores from baseline of the parent study) at each visit
  - Proportion of patients with EASI-90 ( $\geq 90\%$  reduction in EASI scores from baseline of the parent study) at each visit
  - Change and percent change from baseline in Pruritus NRS
  - Proportion of patients with improvement (reduction) of Pruritus NRS  $\geq 3$  from baseline
  - Proportion of patients with improvement (reduction) of Pruritus NRS  $\geq 4$  from baseline
  - Proportion of patients requiring rescue treatment:
    - Overall
    - Systemic treatment
      - Systemic corticosteroids
      - Systemic immunosuppressive drugs

- Phototherapy
- Number of days on topical medication (per patient-year)
- Proportion of patients using topical medications over various periods during the study
- Changes from baseline to prespecified time points through the end of the study:
  - DLQI
  - POEM
  - EQ-5D

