4.6. Safety Variables

4.6.1. Adverse Events and Serious Adverse Events Variables

The primary endpoint in the study is the incidence and rate (events per patient-year) of treatment-emergent adverse events (TEAEs) through the last study visit.

The key secondary endpoints related to AE is

- Incidence and rate (events per patient-year) of SAEs and AEs of special interest

Adverse events and serious adverse events will be collected from the time of informed consent signature and then at each visit until the end of the study. All adverse events are to be coded to a “Preferred Term” and associated primary “System Organ Class (SOC)” according to the Medical Dictionary for Regulatory Activities (MedDRA, latest version).

An **Adverse Event** is any untoward medical occurrence in a patient administered a study drug which may or may not have a causal relationship with the study drug. Therefore, an AE is any unfavorable and unintended sign (including abnormal laboratory finding), symptom, or disease which is temporally associated with the use of a study drug, whether or not considered related to the study drug.

AEs also include: any worsening (i.e., any clinically significant change in frequency and/or intensity) of a pre-existing condition that is temporally associated with the use of the study drug; abnormal laboratory findings considered by the investigator to be clinically significant; and any untoward medical occurrence.

A **Serious Adverse Event** is any untoward medical occurrence that at any dose results in death; is life-threatening; requires in-patient hospitalization or prolongation of existing hospitalization; results in persistent or significant disability/ incapacity; is a congenital anomaly/ birth defect; or is an important medical event.

The criteria for determining whether an abnormal laboratory, vital sign or ECG finding should be reported as an AE are as follows:

- Test result is associated with accompanying symptoms, and/or
- Test result requires additional diagnostic testing or medical/surgical intervention, and/or
- Test result leads to a change in dosing (outside of protocol-stipulated dose adjustments) or discontinuation from the study, significant additional concomitant drug treatment, or other therapy

The pre-treatment period is defined as the period from the subject providing informed consent up to the first dose of study drug in current study.

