Hence any AE with an onset between the end of study visit under protocol amendment 6 and the date of first injection under amendment 7; or between end of study visit under protocol amendment 7 and date of first injection under amendment 8 is **not** considered TEAEs.

The list of adverse events of special interest (AESI) was revised several times. Below is the AESI list under protocol amendments 4 and 5:

- Anaphylactic reactions
- Acute allergic reaction
- Severe injection site reactions that last longer than 24 hours
- Mycosis fungoides
- Cutaneous T-cell dyscrasia
- Any severe infection
- Any infection requiring treatment with parenteral antibiotics
- Any infection requiring treatment with oral antibiotics/anti-viral/anti-fungal for longer than 2 weeks
- Any clinical endoparasitosis
- Any opportunistic infection

Under protocol amendment 6, suicide-related events and certain eye-related events were added as AESIs. Under protocol amendment 7, the list of AESI are as follows:

- Anaphylactic reactions
- Systemic or extensive hypersensitivity reactions
- Malignancy (except basal cell carcinoma)
- Helminthic infections
- Any suicide-related events
- Any type of conjunctivitis or blepharitis, or keratitis (severe or serious)

The SAP summarizes AESIs according to the most current list under protocol amendments 7 and 8. The definition of AESI is same under protocol amendment 7 and 8.

[Appendix 10.6](#) provides a list of AESIs search criteria.

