Any type of conjunctivitis or blepharitis or keratitis (only events that are either severe or serious)	
broad CMQ conjunctivitis (Conjunctivitis, Conjunctivitis allergic, Conjunctivitis bacterial, Conjunctivitis viral, Atopic keratoconjunctivitis, Blepharitis, Dry eye, Eye irritation, Eye pruritus, Lacrimation increased, Eye discharge, Foreign body sensation in eyes, Photophobia, Ocular hyperaemia, Conjunctival hyperaemia, Xerophthalmia);
 
Blepharitis PTs (Blepharitis, blepharitis allergic);
 
Keratitis PTs (Keratitis, Allergic keratitis, Ulcerative keratitis, Atopic keratoconjunctivitis, Herpes ophthalmic, Ophthalmic herpes simplex);
 
AND
 
 • Serious AE= “Yes” OR Severity= “severe” 
Note: manual adjudication of relevant PTs will be required by the study medical monitor, before database lock.

¹ The search criteria are meant to assist the process of identification of TEAE of Special Interest/TEAE Syndrome. However, since these criteria might not be exhaustive in some cases or may not be specific in other cases. Hence an additional review of all PTs in the database may be performed by the Medical monitor, based on medical judgement, to identify any TEAE of Special Interest/TEAE Syndrome that might have been missed by the criteria or to identify any TEAE may be inaccurately assigned as AESI by the algorithmic search

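### SAP 2.0 derives the main-study key secondary AESI endpoint from the amendment 7/8 list and has not been updated to the AESI list in current protocol section 7.2.3

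*SAP*

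**What the plan says.** Both documents make AESIs part of a key secondary endpoint. Protocol 8.2.2 words it as "Incidence and rate (events per patient-year) of SAEs and AESIs" and SAP 4.6.1 as "Incidence and rate (events per patient-year) of SAEs and AEs of special interest". They define the events differently.

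Current protocol 7.2.3 lists six main-study AESIs: anaphylactic reactions, systemic hypersensitivity, helminthic infections, severe conjunctivitis or blepharitis, keratitis (a separate bullet with no severity or seriousness condition), and "Clinically symptomatic eosinophilia (or eosinophilia associated with clinical symptoms". Sites must report them within 24 hours. One injection-site-reaction category is added for the sub-study only.

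SAP 4.6.1 says: "The SAP summarizes AESIs according to the most current list under protocol amendments 7 and 8". Its list includes "Malignancy (except basal cell carcinoma" and "Any suicide-related events", and has no eosinophilia item. The search table in Appendix 10.6 for amendments 6 to 8 follows that list. It has malignancy and suicidal-behaviour rows, no eosinophilia row, and a single eye row headed "Any type of conjunctivitis or blepharitis or keratitis (only events that are either severe or serious".

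**The concern.** An endpoint is defined by the events that qualify for it. If the analysis flag follows one list and the protocol another, the reported AESI incidence and rate are not those of the protocol's endpoint. SAP 5.8.1 reports AESI rates by AESI category, so a category missing from the SAP list gets no row. Events that sites must report as AESIs under the current protocol could then be absent from the AESI tables, while types the protocol no longer treats as AESIs appear in them. The protocol's amendment history attributes the addition of eosinophilia and the removal of malignancy and suicide-related events, both made by amendment 9, to a health authority request. That makes the omission harder to leave standing.

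**Working it through.** The plan gives no figure to reproduce, so the check is an item-by-item comparison of protocol 7.2.3 with SAP 4.6.1 and the amendment 6/7/8 search table in Appendix 10.6.

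| Event type | Protocol 7.2.3 | SAP 4.6.1 and 10.6 | Result |
|---|---|---|---|
| Anaphylactic reactions | AESI | AESI | agree |
| Helminthic infections | AESI | AESI | agree |
| Hypersensitivity | systemic | systemic or extensive (4.6.1); systemic or severe (10.6) | SAP wording wider |
| Conjunctivitis or blepharitis, severe | AESI | AESI | agree |
| Conjunctivitis or blepharitis, serious but not severe | not listed | AESI | SAP only |
| Keratitis, severe or serious | AESI | AESI | agree |
| Keratitis, neither severe nor serious | AESI | not flagged | protocol only |
| Clinically symptomatic eosinophilia | AESI | no category | protocol only |
| Malignancy | not listed | AESI | SAP only |
| Suicide-related events | not listed | AESI | SAP only |

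Apart from the wider hypersensitivity wording, two event types are in the protocol but not the SAP, and three are in the SAP but not the protocol.

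The eye-event rows depend on the SAP condition being severe OR serious. A serious keratitis of moderate severity is therefore counted by both documents; only keratitis that meets neither condition is lost. The same OR brings in serious, non-severe conjunctivitis and blepharitis, which the protocol's severe-only wording leaves out.

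Three other provisions were checked to see whether they close the gap.

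1. The footnote to Appendix 10.6 lets the medical monitor review all preferred terms and reassign events. It is optional, and it is meant to catch events that the search missed or misassigned. It does not create a category that the list lacks.
2. TEAE tables by system organ class and preferred term (SAP 5.8.1) contain the omitted events, but do not identify eosinophilia that was accompanied by symptoms. The eosinophil criterion in Appendix 10.3 is a laboratory threshold only.
3. SAP section 1 allows revision for amendments, SAP section 7 leaves later analyses to an addendum, and protocol section 9 promises a final SAP before database lock. These say where a correction could go, but none makes it.

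On size, the share of keratitis events omitted equals 1 minus the share that is severe or serious. Neither document gives that share, nor any AESI count, so a numerical estimate would only restate whatever share was assumed.

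**The case against.** The strongest reply is that this is timing, not a choice of analysis. SAP 2.0 says it rests on amendments 6, 7 and 8, and it was written for the second-step analysis (cut-off 01 December 2018 for ongoing patients in five countries, database lock planned for 14 February 2019). The amendment 7/8 list was right for that analysis. This stands, and it settles how the point should be described: an SAP that has not been brought up to date. It does not remove the point, because no later SAP is among the documents and version 2.0 is the one that amendment 10 cites.

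Several stronger readings are tempting but unsupported.

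- A reader might infer that the omitted events disappear from the safety results. They do not: they remain TEAEs in the primary endpoint, with exposure-adjusted rates by system organ class and preferred term.
- A reader might infer that all non-severe keratitis is lost. Serious non-severe keratitis is counted.
- Amendment 10 gives "For consistency with the statistical analysis plan (version 2.0" as a rationale, which might be read as endorsing the SAP's AESI list. It is the reason for one change, the removal of Kaplan-Meier and time-to-event analyses. It shows only that version 2.0 was still the reference.
- A reader might infer that the sub-study's primary endpoint, AESI incidence, would be computed with the old list. SAP 2.0 contains no sub-study analysis, and nothing ties that endpoint to the old list.
- Malignancy and suicide-related events might be said to inflate an AESI total. SAP 5.8.1 specifies AESI rates by category and names no pooled total, so a reader could already separate those rows. The omissions matter more than the additions.

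**Conclusion.** The point holds as a mismatch between SAP 2.0 and the current protocol on a key secondary endpoint of the main study. The specified derivation has no category for symptomatic eosinophilia, leaves out keratitis that is neither severe nor serious, and includes three event types that are not protocol AESIs. The direction of each difference is certain from the text; the effect on the reported incidence and rates is unknown. The conclusion assumes that protocol 7.2.3 is meant to govern analyses after the second step and that no later SAP has already made the change. It should be corrected before the next analysis because the correction is cheap and the documents provide for it. It also follows the SAP's own practice: the plan applies the list it regards as most current, and SAP 1.2.3 had already dropped a four-week duration criterion to follow a programme-wide revision.

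**What to change.** In the SAP revision or addendum for any analysis after the second step:

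- Replace the AESI list in 4.6.1 with that of protocol 7.2.3.
- In Appendix 10.6, remove the severity and seriousness filter from the keratitis terms and require severe for conjunctivitis and blepharitis.
- Assign atopic keratoconjunctivitis to one category. It is now in both the conjunctivitis and keratitis term lists, which will carry different filters.
- Add a symptomatic-eosinophilia search with medical-monitor adjudication, since coded terms alone do not establish accompanying symptoms.
- Report malignancy and suicide-related events in separate rows outside the AESI category, so that they stay visible.
- Apply the list to the whole study from coded terms, severity and seriousness, and also show results before and after amendment 9, because accelerated reporting of eosinophilia began only then.
- For the sub-study, state that AESI summaries use the 7.2.3 list with the added injection-site-reaction category, as protocol 7.2.3 and 9.5.6.4 provide.

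The cost is SAP wording, reprogramming of one derived flag, and some extra adjudication under the existing process. The results will not match the second-step AESI tables, and the report should say so.

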4.6.2. Laboratory Safety Variables

Hematology, chemistry, urinalysis, and pregnancy testing samples will be analyzed by a central laboratory.

Blood Chemistry

Sodium	Total protein, serum	Total bilirubin ¹
Potassium	Creatinine	Total cholesterol
Chloride	Blood urea nitrogen (BUN)	Low-density lipoprotein (LDL)
Carbon dioxide	AST	High-density lipoprotein (HDL)
Calcium	ALT	Triglycerides
Glucose	Alkaline phosphatase	Uric acid
Albumin	Lactate dehydrogenase (LDH)	CPK

¹ Direct and indirect bilirubin will be measured when the total bilirubin is above the ULN; CPK isoenzymes will be measured when CPK >5X the ULN

Hematology

Hemoglobin	Differential:
Hematocrit	Neutrophils
Red blood cells (RBCs)	Lymphocytes
White blood cells (WBCs)	Monocytes
Red cell indices	Basophils
Platelet count	Eosinophils

Urinalysis

Microscopic analysis will only be done by the central lab in the event of abnormal dipstick results.

Color	Glucose	RBC
Clarity	Blood	Hyaline and other casts
pH	Bilirubin	Bacteria
Specific gravity	Leukocyte esterase	Epithelial cells
Ketones	Nitrite	Crystals
Protein	WBC	Yeast

Pregnancy serum or urine testing will be performed for all women of childbearing potential.

4.6.3. Vital Sign Variables

The following vital signs parameters will be collected:

- Respiratory rate (bpm)
- Heart rate (bpm)
- Systolic and diastolic blood pressures (mmHg)
- Body temperature (°C) with the measure method (oral/tympanic/axillary/rectal)

Heart rate and blood pressure will be obtained with the patient in sitting position after the patient has rested comfortably for at least 5 minutes. Vital signs will also be taken at 30 (+/- 10) minutes post-injection at visits 2, 3, and 4, during the in-clinic 30-minute post-injection observation.

4.6.4. 12-Lead Electrocardiography (ECG) Variables

Standard 12-Lead ECG parameters include: Ventricular HR, PR interval, QRS interval, corrected QT interval ($QTcF=QT/[RR^{0.33}]$ and $QTcB=QT/[RR^{0.5}]$) ECG status: normal, abnormal not clinically significant or abnormal clinically significant. Electrocardiograms should be performed before blood is drawn during visits requiring blood draws.

ECG measurement was removed from the schedule of events starting from protocol amendment 6.

4.6.5. Physical Examination Variables

A thorough and complete physical examination will be performed. The physical examination variable values are dichotomized to normal and abnormal.

Physical examination was removed from the schedule of events except for the baseline assessment starting from protocol amendment 6.

4.6.6. Ophthalmological Examination

Starting from protocol amendment 6, the ophthalmological examination was added to the schedule of events. This exam will be performed for certain patients of interest, as determined by the sponsor medical monitor in consultation with the investigator, at select study centers that have access and can refer patients to an eye specialist, either a General ophthalmologist or a Cornea and External Eye Disease ('front-of-the-eye') subspecialty expert. Any baseline findings will be documented as part of the patient's medical history and/or physical exam, as appropriate. Any inflammatory ophthalmological condition that occurs post-baseline will be captured as an AE. Additional tests and assessments may be performed to help understand the AEs. The method and procedure for the exam are provided in the study reference manual.

The ophthalmological exam data includes:

- Past ocular history
- Past and current treatment of ophthalmology
- Ophthalmic adverse event assessment
- Ophthalmological examination and procedures
- Intraocular pressure
- Slit lamp biomicroscopy
- Indirect ophthalmoscopy

4.7. Pharmacokinetic (PK) Variables

Samples for drug concentration will be collected at time points according to [Appendix 10.2](#). PK variables consist of functional dupilumab concentration and time (both actual and nominal).

4.8. Antibody (ADA) Variable

ADA variables include the ADA status, titer, neutralizing antibody (NAb) status, and time-point/visit. ADA samples will be collected at the clinic visits according to [Appendix 10.2](#).

4.9. Biomarkers Variables

Research samples, optional genomics substudy, and exploratory biomarker testing assessments was removed from the schedule of events starting from protocol amendment 6. Prior to protocol amendment 6, the following biomarkers were collected in this study:

- TARC
- total serum IgE
- hs-CRP, ANA, anti dsDNA, anti-TPO

Thymus and activation-regulated chemokine and total serum IgE are markers of Th2 activity and are downstream of IL-4/IL-13 signaling. These analytes will be assessed as measures of Th2 activity and drug effect (PD). These results may also be used for modeling dupilumab activity with drug levels in the comparison of dosing regimens. Thymus and activation-regulated chemokine levels have also been closely associated with AD disease activity and severity, and will be evaluated as an exploratory marker of efficacy. These markers may also be assessed for their potential value in predicting treatment response.

Th2 and Th1 immune functions are believed to play a role in regulating each other. To determine whether or not there is a change in non-Th2 mediated inflammation, hs-CRP, as well as autoantibodies anti-dsDNA, anti-TPO, and ANA will be measured.

